3.4 Efficacy Assessment

The ITT Population will be the primary population for the efficacy analysis. Efficacy will also be analyzed using the FAS, the mITT Population, mITT On-Treatment Population, and PP Population as supportive analyses. Primary and secondary efficacy endpoints will be presented in listings.

3.4.1 Primary Efficacy Endpoints

Primary Analysis

The primary efficacy endpoint is the percent change from Day 1 to Day 84 in LDL-C. Co-primary endpoints include the percent change from Day 1 to Day 84 in LDL-C for the obicetrapib 10 mg + ezetimibe 10 mg FDC treatment group compared with each of the following: placebo, ezetimibe 10 mg monotherapy, and obicetrapib 10 mg monotherapy, and for the obicetrapib 10 mg monotherapy treatment group compared with placebo.

Each of the comparisons within the co-primary endpoint family will be conducted at a significance level of 0.05. If and only if all 4 testing achieve statistical significance, the study is claimed to meet its primary objective and the hypothesis testing will continue to secondary endpoints, otherwise all statistical comparisons for secondary endpoints are considered descriptive only.

The LDL-C values measured by preparative ultracentrifugation (PUC) will be used. If the later measurement is not available, the LDL-C values will be assumed missing.

All the analysis for primary efficacy endpoint will be repeated with LDL-C values calculated as follows:

- 1. LDL-C will be calculated using the Friedewald equation unless triglycerides ≥400 mg/dL or LDL-C ≤50 mg/dL; where, LDL-C level will be measured directly by PUC.
- 2. LDL-C will be calculated using the Martin-Hopkins equation unless triglycerides ≥400 mg/dL or LDL-C ≤50 mg/dL; where, LDL-C level will be measured directly by PUC.

Primary Estimand

To assess the primary efficacy endpoint, the primary estimand is defined by the following key attributes:

- **Treatment**: obicetrapib 10 mg + ezetimibe 10 mg FDC treatment versus placebo, ezetimibe 10 mg monotherapy, and obicetrapib 10 mg monotherapy, and obicetrapib 10 mg monotherapy versus placebo
- Target Population: participants who are randomized into the study
- **Analysis Population**: The ITT Population
- Intercurrent events: treatment discontinuation, prohibited medication use

- **Analysis set and handling of intercurrent events**: Treatment policy strategy will be used. All available values of LDL-C at Baseline and Day 84 will be included in the calculation of the percentage change from Baseline to Day 84.
- **Population level summary**: The difference in LS mean percentage change in LDL-C from Baseline to Day 84 between obicetrapib 10 mg + ezetimibe 10 mg FDC treatment versus placebo, ezetimibe 10 mg monotherapy, and obicetrapib 10 mg monotherapy, and obicetrapic 10 mg monotherapy versus placebo

The analysis of covariance (ANCOVA) model with a fixed effect for the treatment group and covariates of Baseline LDL-C will be used to analyze the primary efficacy endpoint. The least squares (LS) mean, standard errors, and 2-sided 95% confidence intervals for each treatment group and for the treatment comparison (FDC treatment – placebo, FDC treatment – ezetimibe 10 mg, and FDC treatment- obicetrapib 10 mg, and obicetrapib 10 mg - placebo) will be provided. Model diagnostics for the ANCOVA model will be computed that include assessment for homogeneity of variance, normality of the residual, and residual outliers. If substantial deviations from the model assumptions are observed, then supportive analyses, such non-parametric assessments, will be considered.

Missing data will be imputed for the primary efficacy analysis based on a pattern mixture model that uses a multiple imputation technique analyzed with ANCOVA with pre-specified fixed factors and covariates. If appropriate, based on the number of retrieved dropouts, missing measurements of non-retrieved dropouts will be modeled by known measurements from retrieved dropouts (i.e., participants who remain in the study after treatment discontinuation) in the same treatment group. If the number of retrieved dropouts is such that the model convergence is questionable and the given parameter estimates cannot be obtained, then missing data at the Day 84 assessment will be estimated based on the placebo treatment group as described in subsequent sections of the SAP corresponding to the first sensitivity analysis.

Missing data at Day 84 will be imputed using a retrieved dropout imputation model assuming the data are missing not at random (MNAR). At Day 84, the data will be split into two groups as follows: (1) all participants that did not discontinue treatment and had a non-missing value at Day 84; and (2) either participants that had a missing value at Day 84, or participants that had discontinued treatment and had a non-missing value at Day 84. For the second group, 100 data sets will be imputed. The imputation model will include LDL-C Baseline and Day 84 values, treatment group. Each data set will be combined with the first group to obtain 100 imputed data sets with no missing values at Day 84. For each imputation data set, the percent change from baseline to Day 84 will be analyzed using the ANCOVA model described above. The results of these 100 analyses will be combined to construct the treatment estimates using the parameter estimates and associated standard errors. Similarly, the difference of the adjusted treatment means will be presented with the associated standard error and two-sided 95% confidence interval. Randomly chosen seed numbers will be selected for the analysis and will be retained.

Sample SAS code is shown below:

1.1

```
Note: Missing value imputation only using participant group (2): participants that had a
missing value at Day 84, or participants that had discontinued treatment and had a non-
missing value at Day 84
TREATMENT = 0 (Placebo), 1 (Obicetrapib), 3(Ezetimibe), 4 (FDC Treatment)
LDLC BASE = Baseline LDL C value
LDLC Day84 = LDL C value at Day 84
proc mi data=LDL_C seed=382794 nimpute=100 out= LDL_C_IMP;
class TREATMENT;
monotone method=reg;
var TREATMENT LDLC_BASE LDLC_DAY84;
     ____
Note: LDL_C_IMP dataset must be merged with dataset containing participants from
group (1): participants that did not discontinue treatment and had a non-missing value at
Day 84.
Note: For each imputation dataset, the percentage change from Baseline to Day 84 will
be analyzed using an ANCOVA approach with a fixed effect for the treatment group and
covariates of Baseline LDL-C.
TREATMENT = 0 (Placebo), 1 (Obicetrapib), 3 (Ezetimibe), 4 (FDC Treatment)
BASE = Baseline LDL C value
PCHG = Percent change from Baseline to Day 84
proc mixed data= TEMP;
by imputation;
class TREATMENT:
model PCHG = TREATMENT BASE / solution cl;
Ismeans TREATMENT / cl diffs;
Note: MI Analyze to combine imputations.
proc mianalyze parms(classvar=full)=mixLSM;
class TREATMENT;
modeleffects TREATMENT;
ods output parameterestimates=mi_LSM;
proc mianalyze parms(classvar=full)=mixDIFF;
class TREATMENT;
modeleffects TREATMENT:
ods output parameterestimates=minus_mi_DIFF;
```

The first sensitivity analysis will be performed imputing missing LDL-C values at Day 84 based on the assumption the data are MNAR using a control-based pattern mixture method. At Day 84, the data will be split into two groups as follows: (1) all participants randomized to the obicetrapib 10 mg + ezetimibe 10 mg FDC treatment, ezetimibe 10 mg monotherapy, and obicetrapib 10 mg monotherapy treatment groups that had a non-missing value at Day 84; and (2) either participants randomized to the placebo treatment group, or participants that had a missing value at Day 84. For the second group, 100 data sets will be imputed. The variables for the imputation model will consist of the LDL-C values from Baseline and Day 84. In this manner, missing data at the Day 84 assessment will be estimated from the placebo treatment group. Each data set will be combined with the first group to obtain 100 imputed data sets with no missing values at Day 84. For each imputation data set, the percent change from baseline to Day 84 will be analyzed using the ANCOVA model described above. The results of these 100 analyses will be combined to construct the treatment estimates using the parameter estimates and associated standard errors. Similarly, the difference of the adjusted treatment means will be presented with the associated standard error and two-sided 95% confidence interval. Randomly chosen seed numbers will be selected for the analysis and will be retained.

The second sensitivity analysis will be performed using the ANCOVA model from the primary analysis for the ITT Population using only observed cases with no imputation for missing data.

The third sensitivity analysis will be performed using ANCOVA model from the primary analysis for the ITT Population using the last observation carried forward (LOCF), i.e. if the Day 84 measurement is missing, then the last on-treatment measurement will be used.

Supplemental Analyses

Supplemental analyses will be performed for the primary efficacy endpoint in order to assess any differences with the results from the primary analysis and investigate what effect, if any, protocol violations have on the trial results. In the first supplemental analysis, a mixed model for repeated measures (MMRM) approach will be utilized. The analysis will include fixed effects for treatment group, visit, and treatment-by-visit interaction, along with covariates of the Baseline LDL-C value as a continuous covariate. The restricted maximum likelihood estimation approach will be used with an unstructured covariance matrix. The LS mean, standard errors, and 2-sided 95% confidence intervals for the treatment group and for the comparison of the treatment groups (FDC treatment vs. placebo, FDC treatment vs. ezetimibe 10 mg, and FDC treatment vs. obicetrapib 10 mg, and obicetrapib 10 mg vs. placebo) will be provided. The MMRM approach will include all available assessments of percent change in LDLC from Day 1, Day 28, and Day 84. The model assumes that the data are missing at random (MAR). If any data are missing, the model will use all information from the other time points to estimate the mean treatment difference at the given time point. No imputation of missing data will be performed. The analysis will be conducted for ITT Population.

Additional supplementary analysis will be performed using the ANCOVA model from the primary analysis based on the FAS, mITT, mITT On-Treatment, and PP populations. No imputation for missing data will be performed for the analysis.

Secondary Estimand

A secondary estimand will be assessed for the primary efficacy endpoint. The secondary estimand is defined by the following key attributes:

- Treatment:

- obicetrapib 10 mg + ezetimibe 10 mg FDC treatment versus placebo,
 ezetimibe 10 mg monotherapy, and obicetrapib 10 mg monotherapy, and obicetrapib 10 mg monotherapy versus placebo
- Target Population: participants who are randomized into the study
- Analysis Population: The ITT Population
- **Intercurrent events**: treatment discontinuation, prohibited medication use
- Analysis set and handling of intercurrent events: A hypothetical strategy will be used. All available values of LDL-C at Baseline and Day 84 will be included in the calculation of the percentage change from Baseline to Day 84.
- **Population level summary**: The difference in LS mean percentage change in LDL-C from Baseline to Day 84 between obicetrapib 10 mg + ezetimibe 10 mg FDC treatment versus placebo, ezetimibe 10 mg monotherapy, and obicetrapib 10 mg monotherapy, and obicetrapic 10 mg monotherapy versus placebo.

This hypothetical estimand represents the treatment effect of FDC treatment relative to placebo, ezetimibe 10 mg monotherapy, and obicetrapib 10 mg monotherapy, and the treatment effect of obicetrapib 10 mg monotherapy relative to placebo at Day 84 in the randomized participants had they remained on their randomized treatment for the entire planned treatment period. This estimand uses a hypothetical strategy to handle intercurrent events and is intended to provide an estimation of the achievable study treatment effect if participants take the treatment as planned. The resulting missing values (corresponding to unobserved values or excluded values following study drug discontinuation or the use of prohibited medication) will be implicitly handled by using a MMRM approach under the assumption of missing at random. The model will be similar to the MMRM approach described previously for the supplemental analysis of the primary efficacy endpoint. The supplementary analysis for the primary efficacy endpoint assessed by secondary estimand will be performed using the mITT On-Treatment populations.

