3.1.4 Coronavirus Disease 2019 Contingency Measures

In cases of COVID-19 limitations, it is the Investigator's responsibility to assure the safety of participants. If necessary, the Sponsor will implement and document mitigation strategies. At the Investigator's discretion, the study visit(s) can be conducted in-clinic or virtually. If conducted virtually, the visit will include alternative methods for safety, efficacy, and distribution/collection of study drugs, including but not limited to phone/video contact, alternative location for biologic sample collection, alternative secure delivery of study drugs, home health care (if available), and a secured way of transferring participant data from and to home health services and the site.

If these contingency measures occur, the Sponsor will document the changes made, communicate recommendations about such changes in a timely fashion to minimize or prevent disruptions to the study, and support sites in implementing these changes. Documentation of these cases and the site's management of participants should be recorded in the Investigator study files. In the absence of a COVID-19 impact, it is expected that Investigators and participants follow the protocol requirements as set forth.

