 - For any participant not taking statin therapy due to statin intolerance, including those participants taking bempedoic acid or fibrate monotherapy, written confirmation will be required of both the participant and the Investigator stating that the participant is statin intolerant, aware of the benefit of statins to reduce the risk of a MACE, and aware that many other patients who are unable to tolerate a statin were actually able to tolerate a different statin or dose.

Note: Statin intolerance will be defined as intolerance due to an adverse safety effect that started or increased during statin therapy and resolved or improved when statin therapy was discontinued, resulting in an inability to tolerate either 1) two or more statins at any dose, or 2) one statin at any dose and either an unwillingness to attempt a second statin or advice by a physician not to attempt a second statin.²⁵

- o Bempedoic acid for at least 8 weeks in combination with a maximally tolerated statin prior to Screening (Visit 1); and/or
- A PCSK9-targeted therapy alone or in combination with other lipid-modifying therapy for at least 4 doses prior to Screening (Visit 1).

Note: Patients taking inclisiran must have received at least 2 stable doses prior to Screening.

Note: Approximately 70% of the participants enrolled into this study should be taking HIS. No more than approximately 10% of participants in this study will be completely statin intolerant. Documentation in the electronic case report form (eCRF) of the reason why a participant is unable to take HIS is required. HIS include atorvastatin 40 and 80 mg and rosuvastatin 20 and 40 mg.

5. Have a fasting serum LDL-C at Screening (Visit 1) \geq 70 mg/dL (\geq 1.8 mmol/L);

Note: For eligibility purposes, LDL-C at Screening (Visit 1) will be calculated using the Martin-Hopkins equation unless TG \geq 400 mg/dL (\geq 4.5 mmol/L) or LDL-C \leq 50 mg/dL (\leq 1.3 mmol/L); in both cases, LDL-C level will be measured directly by preparative ultracentrifugation, also referred to as beta quantification.²⁶

- 6. Have fasting TG <500 mg/dL (<5.7 mmol/L) at Screening (Visit 1); and
- 7. Have an estimated glomerular filtration rate (eGFR) ≥15 mL/min/1.73 m² calculated using the Chronic Kidney Disease Epidemiology Collaboration equation²⁷ at Screening (Visit 1).

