7.1.2 Lipid Profile/Biomarkers

Blood samples for the lipid profile must be obtained under fasting conditions (ie, after the participant has fasted for a minimum of 8 hours) and before study drug administration. For the purposes of this study, fasting will be defined as nothing by mouth except water and any essential medications. If a participant is not fasting, the Investigator should reschedule the visit as soon as possible.

LDL-C level will be calculated using the Martin-Hopkins and Friedewald equations unless TG ≥400 mg/dL (≥4.5 mmol/L) or LDL-C ≤50 mg/dL (≤1.3 mmol/L); in both cases, LDL-C level will be measured directly by preparative ultracentrifugation, also referred to as beta quantification. Additionally, LDL-C will be measured by preparative ultracentrifugation at Visit 2 (Day 1), Visit 4 (Day 84), and, in cases of early discontinuation of study drug or study, at an EOT Visit, for all participants.

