3.1.3 Definition of Baseline

Baseline is defined as the last measurement prior to the first dose of study drug, unless otherwise stated.

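### Setting LDL-C to missing whenever the ultracentrifugation result is absent drops some treated participants from the primary analysis and imputes others as dropouts, although a same-visit calculated LDL-C normally exists

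*SAP*

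**What the plan says.** **Method for the primary endpoint.** SAP 3.4.1 states: "The LDL-C values measured by preparative ultracentrifugation (PUC) will be used". The next sentence gives the rule for an absent result: "If the later measurement is not available, the LDL-C values will be assumed missing". Here *later* must mean *latter*, that is, the PUC value. All primary-endpoint analyses are then repeated with Friedewald and with Martin-Hopkins LDL-C.

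**What is collected.** Protocol 7.1.2: "LDL-C level will be calculated using the Martin-Hopkins and Friedewald equations unless TG" is at least 400 mg/dL or LDL-C is at most 50 mg/dL, in which cases PUC is used. It continues: "Additionally, LDL-C will be measured by preparative ultracentrifugation at Visit 2 (Day 1), Visit 4 (Day 84), and, in cases of early discontinuation", at an EOT visit. The schedule of procedures places a fasting lipid profile at Screening, Day 1, Day 28 and Day 84. At Screening PUC is not routine (Protocol 4.1): "For eligibility purposes, LDL-C at Screening (Visit 1) will be calculated using the Martin-Hopkins equation unless TG" or LDL-C crosses the same limits.

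**Baseline.** SAP 3.1.3: "Baseline is defined as the last measurement prior to the first dose of study drug, unless otherwise stated". Protocol 9.2 says last non-missing.

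**Imputation.** SAP 3.4.1 imputes Day 84 only. Group (1), which is not imputed, is "all participants that did not discontinue treatment and had a non-missing value at Day 84". Group (2) holds participants with Day 84 missing, plus discontinued participants with Day 84 observed. The imputation variables are treatment, baseline and Day 84 LDL-C. If there are too few retrieved dropouts, missing Day 84 values are estimated from the placebo group.

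**The concern.** The SAP accepts the calculated LDL-C as good enough to rerun every primary-endpoint analysis. In the primary analysis itself it gives that value no role, even as a predictor, when the PUC result from the same visit is absent. Two things follow.

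- **Day 1 PUC lost.** The participant has no PUC baseline, so neither the percent change nor the covariate can be formed. The analysis is described as covering all randomized participants, yet this participant leaves it and the SAP does not say so.
- **Day 84 PUC lost.** A participant who stayed on drug is treated like someone who stopped. The Day 84 value is drawn from retrieved dropouts in the same arm, or from placebo under the fallback, although LDL-C was normally obtained that day by equation.

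All four co-primary comparisons must succeed, so the narrowest one, FDC versus obicetrapib, is where any loss matters most.

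**Working it through.** **1. The plan's own figure.** Inputs from SAP 2.2.2: 95 evaluable per arm, difference 12 points, SD 25, 1-sided 0.025. Two-sample t test with noncentrality 12 / (25 × √(2/n)) and 2n − 2 degrees of freedom. At n = 95: 12 / (25 × 0.1451) = 3.31, df 188, power 90.8% (91.1% by the normal approximation). The stated figure of more than 90% is reproduced. The other comparisons (15, 20 and 30 points) have at least 98% power. Enrolment: 380 / 0.95 = 400, as planned.

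**2. Tracing the rule by pattern (PUC values).**

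| Day 1 PUC | Day 84 PUC | Treatment | What the SAP does |
|---|---|---|---|
| absent | present | on drug | Group (1), not imputed, no percent change, leaves the ANCOVA |
| present | absent | on drug | Group (2), imputed from retrieved dropouts, or from placebo under the fallback |
| absent | absent | any | Group (2); the sample code would impute both values |
| absent | present | discontinued | Group (2), non-monotone pattern that the monotone regression step does not cover |

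The first row assumes no Screening PUC, which exists only if TG was ≥400 or LDL-C ≤50 mg/dL. The second assumes no usable unscheduled repeat under SAP 3.1.2.

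A synthetic data set of 400 confirms the first row. It had 5 discontinuations per arm (2 of them without Day 84) and 2 on-treatment participants per arm without a Day 1 PUC. The split gave 380 in group (1) and 20 in group (2). All 8 without a baseline were in group (1), and the ANCOVA used 400 − 8 = 392 rows.

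**3. How many.** The documents give no PUC failure rate. Assume 2-5% of results are lost at each visit while the panel is reported:

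- Day 1: 400 × 0.02 = 8 to 400 × 0.05 = 20 dropped, or 2-5 per arm.
- Day 84: a further 8-20 imputed. These do not reduce n.

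**4. Power for the 12-point comparison after Day 1 losses.** Same formula.

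| Entering per arm | No loss | 2 lost | 5 lost |
|---|---|---|---|
| 100 | 92.2% | 91.7% (n = 98) | 90.8% (n = 95) |
| 95 | 90.8% | 90.3% (n = 93) | 89.3% (n = 90) |

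The primary analysis imputes dropouts, so up to 100 per arm enter it. Imputed rows carry less information than observed ones, so the truth lies between the two lines.

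**5. Effect of the Day 84 route.** Under the placebo fallback, if a fraction f of each active arm is replaced by placebo-like values, a difference between two active arms shrinks by the factor 1 − f: 12 × 0.98 = 11.8 points to 12 × 0.95 = 11.4 points. Step 4 does not include this.

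**The case against.** A single-method primary endpoint is a legitimate prespecified choice, and the SAP states its rule openly. Several safeguards also exist.

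- **Repeats.** The Martin-Hopkins and Friedewald repeats bring affected participants back, so the effect of leaving them out can be seen. This stands as mitigation, but those repeats do not decide whether the trial succeeds.
- **Unscheduled samples.** SAP 3.1.2 substitutes the nearest unscheduled measurement when scheduled results are unreportable. That covers part of the Day 84 problem if the repeat includes PUC. It cannot restore a baseline once dosing has begun.
- **General wording.** SAP 3.1.7 says missing primary-endpoint values are multiply imputed, but the method it points to covers Day 84 only. The baseline definition might be read as admitting a Screening Martin-Hopkins value, but the PUC-only rule in 3.4.1 excludes that.
- **Frequency.** A reader might infer from Protocol 3.1.4, which allows "alternative location for biologic sample collection", that missing PUC results are to be expected. The text does not say PUC would be skipped there, and a missed draw loses both results. The concern needs the narrower case of a PUC result lost while the panel is reported, and no passage shows that to be common.
- **Bias.** A reader might infer that the Day 1 exclusions bias the comparison or defeat the ITT analysis. The documents do not support this: the Day 1 sample precedes study drug, so its loss cannot result from treatment. The exclusion costs precision and should be declared.

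**Conclusion.** The point holds, at modest size. SAP 3.4.1 as written removes on-treatment participants without a Day 1 PUC from an analysis described as all-randomized. It also imputes on-treatment participants without a Day 84 PUC as if they had dropped out or taken placebo. Both follow from the text and need no assumed rate; only the counts do. At an assumed 2-5% loss per visit, 8-20 participants are dropped and a further 8-20 imputed.

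A reader might add these to 16-40 lost and set that against the 20 dropouts allowed for. That would be wrong, because only the Day 1 losses reduce n. Nor do the documents support a claim that the trial becomes underpowered: through loss of n alone, the 12-point comparison stays above 90% from 100 per arm and reaches 89.3% at worst from 95.

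The reasons to act are the undeclared exclusion and the use of dropout- or placebo-based values for treated participants whose LDL-C was normally available by another method that day.

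**What to change.** Keep PUC as the primary endpoint and replace the missing-value sentence in SAP 3.4.1 along these lines, before unblinding:

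- If PUC is unavailable at Day 1 or Day 84 but the same-visit Martin-Hopkins value is available, impute the PUC value within the multiple imputation by regression on that value, fitted in participants who have both. PUC remains the scale at both visits, so methods are not mixed within one percent change.
- Use the retrieved-dropout model, and its placebo fallback, only for visits with neither result.
- State that a Screening Martin-Hopkins value does not serve as the PUC baseline, and correct *later* to *latter*.

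If the sponsor prefers no between-method imputation, the SAP should at least say how a missing Day 1 PUC is handled and report how many participants it affects.

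**Cost.** SAP wording and one more variable in the imputation step; no new data. A few values would rest on a between-method regression. The calculated value may also not be reported at Day 84 when LDL-C is ≤50 or TG ≥400 mg/dL, and low LDL-C is probably most frequent in the FDC arm. The fix therefore helps less at Day 84 than at Day 1, where entry required LDL-C of at least 70 mg/dL at Screening. The SAP should disclose both limits.

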2.2.2 Sample Size Determination

A sample size of at least 380 evaluable participants (ie, 95 participants per treatment group) will provide more than 90% power to detect a 30% difference in LDL-C reduction at Day 84 (SD of 25%) for the obicetrapib 10 mg + ezetimibe 10 mg FDC treatment group compared with the placebo group at a 1-sided significance level of 0.025.

The sample size for this study was determined in order to provide sufficient power (>90%) for the analyses of the co-primary endpoints described above. A sample size of at least 380 evaluable participants (ie, 95 participants per treatment group) will provide more than 90% power to detect a 20% difference in LDL-C reduction at Day 84 for the obicetrapib 10 mg + ezetimibe 10 mg FDC treatment group compared with the ezetimibe 10 mg monotherapy treatment group, and it will provide more than 90% power to detect a 12% difference in LDL-C reduction at Day 84 for the obicetrapib 10 mg + ezetimibe 10 mg FDC treatment group compared with the obicetrapib 10 mg monotherapy treatment group, assuming an SD of 25% at a 1-sided significance level of 0.025.

In addition, the sample of 95 participants in the obicetrapib 10 mg monotherapy treatment group will provide more than 90% power to detect a 15% difference in LDL-C reduction at Day 84 compared with the placebo treatment group.

Therefore, assuming an approximately 5% dropout rate, enrollment of approximately 400 participants (ie, 100 participants per treatment group) is planned for this study. This sample size will also contribute sufficient participant exposure and safety data.

Table 1 Schedule of Procedures

	Screening ^{a,b} Treatment Period Sa		Safety Follow-Up			
Visit	1	2	3	4	5	
Week	Up to -2	0	4	12	16	EOT ^c
Day (±Visit Window)	-14 to -1	1	28 (±7)	84 (±7)	112 (±7)	_
Informed consent ^d	X					
Inclusion/exclusion criteria	X	Xe				
Demographic information	X					
Medical/surgical history	X					
Prior/concomitant medications	X	X	X	X	X	X
Weight and height ^f	X					
Physical examination ^g	X			X		X
Vital signs ^h	X	X	X	X	X	X
12-lead ECG ⁱ	X					
Urine pregnancy test ^j	X			X		X
FSH test ^k	X					
Fasting chemistry and hematology ¹	X	X	X	X	X	X
Coagulation parameters	X			X		X
Fasting lipid profile ^m	X	X	X	X		X
Fasting Lp(a) ⁿ		X		X		X
Urine sample for UACR	X	X	X	X	X	X
Pharmacokinetics ^o		X	X	X		X
Serum archive sample ^p		X		Xq		X
Randomization		X				
Dispense study drugs ^r		X	X			
Study drug administration ^s						
Study drug compliance			X	X^q		X

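### The primary ANCOVA tests each pair of arms with one residual variance pooled over four arms, so the FDC-versus-obicetrapib test can drift from its 5% level in either direction if arm variances differ; a variance-robust model could be prespecified at almost no cost.

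*SAP*

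**What the plan says.** SAP section 3.4.1 (Primary Efficacy Endpoints) fits one ANCOVA of percent change in LDL-C to all four arms, with treatment as a fixed effect and baseline LDL-C as covariate. The pairwise LS-mean differences come from that single fit. In the sample code the model statement is "model PCHG = TREATMENT BASE / solution cl", run in PROC MIXED on all four treatment codes. No REPEATED / GROUP= statement and no empirical (sandwich) option is shown, so there is one residual variance. The fit is repeated in each of 100 imputed data sets and combined with PROC MIANALYZE.

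On error control the same section says: "Each of the comparisons within the co-primary endpoint family will be conducted at a significance level of 0.05". The intervals are two-sided 95%, and all four comparisons must be significant for the primary objective to be met.

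On assumptions, the section plans diagnostics for homogeneity of variance, normality and outliers, without naming a test or threshold. The response to a failure is: "If substantial deviations from the model assumptions are observed, then supportive analyses, such non-parametric assessments, will be considered".

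The three sensitivity analyses reuse the same ANCOVA. The supplemental MMRM has a covariance matrix that is unstructured over visits, and no arm-specific covariance is mentioned. SAP section 3.4.2 applies similar ANCOVA models to the secondary endpoints, two of which are again FDC versus obicetrapib.

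For planning, SAP section 2.2.2 uses one SD for every arm: "assuming an SD of 25% at a 1-sided significance level of 0.025". For FDC versus obicetrapib it states that "it will provide more than 90% power to detect a 12% difference in LDL-C reduction at Day 84".

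**The concern.** With equal arm sizes, the usual reassurance is that a pooled-variance test keeps its level even when variances differ. That holds for two arms, because the pooled variance is then the average of the two variances in the contrast. In a four-arm model the pooled variance also averages in two arms that play no part in the contrast. If FDC and obicetrapib are more variable than placebo and ezetimibe, the standard error of their difference is too small and the test too liberal. If they are less variable, the test is too conservative and power is lost.

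FDC versus obicetrapib shows what ezetimibe adds to obicetrapib. It has the smallest planned effect and the lowest power of the four comparisons. The confidence interval reported for that difference would carry the same error as the p-value.

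The plan anticipates the problem by checking for it, but it leaves the primary p-value and interval on the pooled variance whatever the check shows. A non-parametric supportive analysis would not by itself restore the level of the primary test.

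**Working it through.** **Inputs from the documents.** 95 evaluable per arm; allocation 1:1:1:1; common SD 25; planned differences of 30 (FDC–placebo), 20 (FDC–ezetimibe), 12 (FDC–obicetrapib) and 15 points (obicetrapib–placebo); one-sided 0.025 for sample size, which matches two-sided 0.05 in the analysis.

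**Inputs assumed.** Arm-specific SDs. The documents give none.

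**Step 1: the plan's own figures.** SE = 25 × √(2/95) = 3.627, and power = Φ(difference/SE − 1.96).

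- 12 points: 12/3.627 = 3.308; Φ(1.348) = 91.1% (90.8% to 91.0% with the noncentral t)
- 15 points: Φ(4.135 − 1.96) = 98.5%
- 20 points: Φ(5.514 − 1.96) = 99.98%
- 30 points: above 99.9%
- Enrollment: 380/0.95 = 400

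All stated figures reproduce.

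**Step 2: level under a pooled variance.** With equal n, the model's residual variance estimates the mean of the four arm variances, V4. The true variance of FDC minus obicetrapib depends on V2, the mean of those two arms' variances. So

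level = 2 × [1 − Φ(1.96 × √(V4/V2))].

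Worked case, SD 28 in the two obicetrapib-containing arms and 22 in the other two: V4 = (784 + 784 + 484 + 484)/4 = 634; V2 = 784; √(634/784) = 0.899; 1.96 × 0.899 = 1.763; level = 7.8%.

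| SD, obicetrapib-containing / other arms | V4 | V2 | Two-sided level |
|---|---|---|---|
| 25/25 | 625 | 625 | 5.0% |
| 26/24 | 626 | 676 | 5.9% |
| 28/22 | 634 | 784 | 7.8% |
| 30/20 | 650 | 900 | 9.6% |
| 22/28 | 634 | 484 | 2.5% |
| 20/30 | 650 | 400 | 1.2% |

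Less regular patterns (placebo/ezetimibe/obicetrapib/FDC) give 5.7% at 25/25/25/28, 6.9% at 22/24/26/28 and 5.1% at 25/25/22/28.

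**Step 3: simulation.** Complete-data four-arm ANCOVAs with 95 per arm gave 7.7% at 28/22, 8.7% to 9.8% at 30/20 over separate runs, and 1.4% at 20/30. This agrees with the formula.

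**Step 4: other consequences.**

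- At 30/20 the nominal 95% interval for FDC minus obicetrapib covers about 90.5%.
- In the patterns tabulated, each of the other three comparisons pairs one arm of each kind, so V2 = V4 and their level stays near 5%. This is not general: at 20/20/25/35 the levels are 9.6% (FDC–obicetrapib), 7.6% (FDC–placebo and FDC–ezetimibe) and 2.5% (obicetrapib–placebo).
- With FDC equal to obicetrapib and the other three differences large (35, 15 and 35 points), the simulated chance of passing all four tests was 5.0% at 25/25, 8.1% at 30/20 and 1.3% at 20/30.

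**Step 5: with a robust standard error.** Heteroscedasticity-consistent (HC3) standard errors gave simulated levels between 4.0% and 5.2% over the patterns run. Power for 12 points with a variance from the two arms alone, against the pooled variance:

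- 25/25: 90.9% against 91.0%
- 20/30: about 98% against about 95%
- 30/20: about 78% against about 86%. The higher pooled figure is obtained at the inflated level.

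**The case against.** The strongest objection is that the premise is not in the documents. The only SD given is a common 25%, and nothing says that arms differ, in which direction or by how much. Any pooled multi-arm ANCOVA has this conditional property. This stands: a reader might infer from the 7.8% and 9.6% figures that the primary test is known to be too liberal, and the documents do not support that. Mild departures leave the level between 5% and 7%, and the conservative direction is just as open.

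Second, the plan does prespecify the check. Non-parametric methods are only an example of a response, the code is labelled as a sample, and detailed programming specifications sit in a separate document (SAP section 6). Keeping the prespecified primary test and treating alternatives as supportive also avoids a data-driven switch. This stands in part. It argues for fixing the variance model in advance; it does not show that the primary standard error is protected now, and neither document says that it is.

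Third, the inflated level matters for a false claim only if ezetimibe adds nothing to obicetrapib. Protocol section 1.5.1 cites LDL-C reductions of 18.58% for ezetimibe against placebo and 15.1% on top of a statin. This lowers the practical stakes for the all-four rule but leaves the interval's coverage affected. It also tells against the inference that this one comparison decides the trial. It has the lowest power, but all four must pass.

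Fourth, the calculations use complete data, while the planned analysis uses multiple imputation. This stands as a limit. With about 5% dropout the effect is probably small, but it has not been quantified.

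**Conclusion.** The point holds in a conditional form. The primary analysis relies on a variance pooled over four arms for pairwise tests, and nothing in the plan corrects the primary standard error if the arms differ in variability. Under the assumed SDs in the table the two-sided level of FDC versus obicetrapib runs from 1.2% to 9.6%, and it is 5.0% when SDs are equal. These figures rest on assumed SDs, complete data and 95 per arm, so they are neither a prediction nor the level of the imputation-based analysis. The documents do not show the plan to be wrong as written. This is an inexpensive improvement to make before unblinding; changing the primary standard error after a failed diagnostic would look data-driven.

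**What to change.** State in SAP section 3.4.1 that the primary model allows a separate residual variance for each arm (REPEATED / GROUP=TREATMENT in PROC MIXED) or uses heteroscedasticity-consistent standard errors. Combine the resulting estimates and standard errors over the 100 imputations by Rubin's rules. Satterthwaite or Kenward-Roger degrees of freedom from PROC MIXED do not pass automatically into the PROC MIANALYZE calls shown, so the SAP should also say which complete-data degrees of freedom are supplied there (EDF=). Carry the same choice into the ANCOVAs for the secondary endpoints. The pooled-variance version can be kept as a sensitivity analysis.

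The cost is a few lines of SAS and one SAP sentence. If variances are equal, power for the 12-point difference moves from about 91.0% to 90.9%. No change to sample size or conduct is needed.
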